Appendix 2. Health-Related Quality of Life Measures

Patient-Reported Outcomes Measurement Information System (PROMIS) – Adult

Patient-Reported Outcomes Measurement Information System (PROMIS) – Pediatric

[figure not shown]
Patient-Reported Outcomes Measurement Information System (PROMIS) – Parent Proxy

Patient Global Impression of Change (PGIC)

Clinical Global Impression of Change (CGIC)

PROMIS-43 Profile v2.1

[figure not shown]
COPYRIGHTED MATERIAL

19 September 2017
© 2008-2017 PROMIS Health Organization (PHO) Page 1 of 3

[figure not shown]
PROMIS-43 Profile v2.1

COPYRIGHTED MATERIAL

PROMIS-43 Profile v2.1

COPYRIGHTED MATERIAL

[figure not shown]

19 September 2017
© 2008-2017 PROMIS Health Organization (PHO) Page 3 of 3

PROMIS® Pediatric Profile v2.0 – Profile-37

[figure not shown]
Pediatric Profile- 37

COPYRIGHTED MATERIAL

PROMIS® Pediatric Profile v2.0 – Profile-37

COPYRIGHTED MATERIAL

7 July 2020

© 2010-2020 PROMIS Health Organization (PHO)

Page 2 of 3

Pfizer Confidential

CT24-WI-GL02-RF02 5.0 Non-Interventional Study Protocol Template For Secondary Data Collection Study
01-Aug-2023
Page 58 of 64

PROMIS® Pediatric Profile v2.0 – Profile-37

[figure not shown]
COPYRIGHTED MATERIAL

PROMIS® Parent Proxy Profile v2.0 – Profile-37

Parent Proxy Profile – 37

[figure not shown]
COPYRIGHTED MATERIAL

21 February 2020
© 1010-2020 PROMIS Health Organization (PHO) Page 1 of 3

PROMIS® Parent Proxy Profile v2.0 – Profile-37

COPYRIGHTED MATERIAL

PROMIS® Parent Proxy Profile v2.0 – Profile-37

COPYRIGHTED MATERIAL

Patient Global Impression of Change (PGIC)

| | |
|--|--|
| Not Done |  |
| * Not Done, Reason |  |
| * Date of assessment |  (DD-MMM-YYYY) |
| * Compared to your condition at the start of the study, how much have you changed? | 
 VERY MUCH IMPROVED MUCH IMPROVED MINIMALLY IMPROVED NO CHANGE MINIMALLY WORSE MUCH WORSE VERY MUCH WORSE |
| How has this assessment been performed? | 
 PARTICIPANT SELF-REPORT PARENT PROXY |

Clinical Global Impression of Change (CGIC)

* Date of assessment

(DD-MMM-YYYY)

* Compared to the subject's condition prior to treatment, how much has the subject's condition changed?

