Regardless of how long participants have been on Oxbryta® (Voxelotor) when they enroll in the study, participants will be followed for up to 5 years after their first dose of Oxbryta® (Voxelotor) treatment, or until they withdraw their consent to participate, or are discontinued from the study. Treatment, including interruptions and restarting treatment, will continue at the discretion of the treating physician, and there are no pre-defined treatment requirements. Participants may receive any additional medications prescribed by their treating physician or have any medical interventions that are deemed appropriate by the treating physician or study doctor. The participant or treating physician may discontinue Oxbryta® (Voxelotor) at any time. Participants who discontinue treatment with Oxbryta® (Voxelotor) earlier than 5 years will continue to be followed on study to collect clinical and health-related quality of life (HRQoL) outcomes for up to 5 years after their first dose of Oxbryta® (Voxelotor) treatment.

Participant safety and tolerability will be assessed throughout the study data collection period by the study doctor and reported to the Sponsor.

The overall study design is illustrated in [Figure 1](#).

Figure 1: Study Schema

SOC, standard of care.

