9.14.2. Study and Site Start and Closure

9.14.2.1. First Act of Recruitment

The study start date is the date on which the study is open for recruitment of participants.

The first act of recruitment is the first site open and will be the study start date.

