3.2 Effectiveness Endpoint Measures

- Change from pre-Oxbryta® (Voxelotor) treatment period in the following hematologic parameters:
 - Hb
 - Hemolysis measures, including % reticulocytes, absolute reticulocytes, bilirubin (total, direct, and indirect)
 - Measures of iron overload, including ferritin, T2-weighted magnetic resonance imaging (T2*MRI)
- Change from pre-Oxbryta® (Voxelotor) treatment period in renal function, as measured by the following:
 - Creatinine (Serum)
 - Albuminuria (urine albumin/creatinine ratio [ACR])
 - Hemoglobinuria (urine dipstick positive for blood +1 or greater and ≤ 2 RBC by high power field)
 - Serum cystatin C

PFIZER CONFIDENTIAL

CT24-WI-GL03-RF03 3.0 *Non-Interventional Statistical Analysis Plan*
for Secondary Data Collection Study

- Estimated glomerular filtration rate (eGFR) calculated using the Chronic Kidney Disease Epidemiology Collaboration (CKD-EPI) equation
- Rate of significant SCD complications, for example acute pain crisis, acute chest syndrome (ACS), priapism, stroke, and transient ischemic attack (TIA), chronic or end stage kidney disease, iron overload, leg ulcers, cardiac malfunction, and pulmonary hypertension (PH)
- Treatment initiation or modification of SCD-related medications (eg, hydroxyurea, crizanlizumab, L-glutamine, opioids [in daily morphine equivalents], iron chelating agents, erythropoiesis-stimulating agents [ESAs], nonsteroidal anti-inflammatory drugs [NSAIDs], folic acid, and penicillin)
- Change from pre-Oxbryta® (Voxelotor) treatment period in HCRU: rate of outpatient visits (including infusion center, acute care, or telemedicine visit), emergency department (ED) visits, hospitalizations (including total length of stay and time in intensive care unit [ICU], if applicable), acute and chronic RBC transfusions, home oxygen supplementation, and renal dialysis
- Change from pre-Oxbryta® (Voxelotor) treatment period in the following HRQoL measures:
 - Patient-Reported Outcomes Measurement Information System (PROMIS) 42 item (adults) and 39 item (children/ adolescents)
 - Patient Global Impression of Change (PGIC)
 - Clinical Global Impression of Change (CGIC)
 - Other measures: Acute pain intensity as measured by Numerical Pain Rating Scale (NPRS) and any objective measure of exercise tolerance.

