4.7.1. Index date and follow-up

The index date is defined as the inform consent date. The Post Oxbryta period is from the first dose of Oxbryta to the date of end of treatment or end of study.

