- Change from pre-Oxbryta treatment period in the following Chemistry parameters corresponding to treatment with Oxbryta® (Voxelotol):
 - Ferritin

Analysis: Observed and change from pre-Oxbryta treatment period on ferritin will be summarized descriptively ([Section 4.7](#)) by visit.

- Change from pre-Oxbryta® (Voxelotol) treatment period in renal function:
 - Creatinine (Serum)
 - Albuminuria (urine albumin/creatinine ratio [ACR])
 - Hemoglobinuria (urine dipstick positive for blood +1 or greater and ≤ 2 RBC by high power field)
 - Serum cystatin C
 - Estimated eGFR calculated using the CKD-EPI equation

Analysis: Observed and change from pre-Oxbryta treatment period on Creatinine (Serum), Albuminuria, Hemoglobinuria, Serum cystatin C and eGFR will be summarized descriptively ([Section 4.7](#)) by visit

- Rate of SCD complications including acute pain crisis, acute chest syndrome

(ACS), priapism, stroke, and transient ischemic attack (TIA), chronic or end stage kidney disease, iron overload, leg ulcers, cardiac malfunction, and pulmonary hypertension (PH) and RBC transfusions.

Analysis:

The number and percentage of participants with SCD complications including acute pain crisis, ACS, priapism, stroke, chronic or end stage kidney disease iron overload, leg ulcers, cardiac malfunction and PH and RBC transfusions will be summarized by SOC and PT throughout the treatment period.

The annualized incidence rate of SCD complications including acute pain crisis, ACS, priapism, stroke, chronic or end stage kidney disease iron overload, leg ulcers, cardiac malfunction and PH and RBC transfusions will be summarized by SOC and PT throughout the treatment period.

- **PGIC**

PGIC includes 7 response categories: Very much improved, much improved, minimally improved, no change, minimally worse, much worse and very much worse.

Analysis: The PGIC will be summarized as numbers and percentages by visit for each response category.

- **CGIC**

CGIC includes 7 response categories: Very much improved, much improved, minimally improved, no change, minimally worse, much worse and very much worse.

Analysis: The CGIC will be summarized as numbers and percentages by visit for each response category.

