6. APPENDICES

6.1. Appendix A: List of tables

Table/Listing	Title	Endpoint
Table 15.1.1	Summary of Participant Disposition - Full Analysis Set	Disposition
Table 15.1.2	Demographics and Baseline Characteristics - Full Analysis Set	Baseline
Table 15.1.3	Medical History – Full Analysis Set	Medical history

Table 15.1.4	Study Drug Administration - Safety Analysis Set	Exposure
Table 15.1.5	Study Drug Administration and Dosage Changes Initiated by the Physician - Safety Analysis Set	Exposure
Table 15.2.1	Change in Hematologic Laboratory -Hb Tests by Visit - Full Analysis Set	Effectiveness
Table 15.2.2	Change in Hematologic Laboratory -Hemolysis measures by Visit - Full Analysis Set	Effectiveness
Table 15.2.3	Change in Chemistry Laboratory - Chemistry measures by Visit - Full Analysis Set	Effectiveness
Table 15.2.4	Change in Renal Function Laboratory Tests by Visit - Full Analysis Set	Effectiveness
Table 15.2.5	Summary of SCD Complications-Full Analysis Set	Effectiveness
Table 15.2.5.1	Summary of Transfusions -Full Analysis Set	Effectiveness
Table 15.2.6	Annualized Incidence Rate of SCD Complications - Safety Analysis Set	Effectiveness
Table 15.2.6.1	Annualized Incidence Rate of Transfusions - Safety Analysis Set	Effectiveness
Table 15.2.7	Summary of Patient Global Impression of Change (PGIC) – Full Analysis Set	HRQoL
Table 15.2.8	Summary of Clinical Global Impression of Change (CGIC) – Full Analysis Set	HRQoL
Table 15.3.1	Treatment Emergent Adverse Events by System Organ Class and Preferred Term by Severity - Safety Analysis Set	Safety
Table 15.3.2	Treatment Related Treatment Emergent Adverse Events by System Organ Class and Preferred Term by Severity- Safety Analysis Set	Safety

Table 15.3.3	Treatment Emergent Serious Adverse Events by System Organ Class and Preferred Term by Severity - Safety Analysis Set	Safety
Table 15.3.4	Pregnancy Outcomes and Fertility listings - Safety Analysis Set	Safety
Table 15.3.5	Individual Listings of Deaths- Safety Analysis Set	Safety
Table 15.3.6	Listing of AEs Leading to Discontinuation of the Study - Safety Analysis Set	Safety
Table 15.3.7	Individual Listing of SAEs - Safety Analysis Set	Safety
Table 15.4	Listing of Concomitant Medication - Safety Analysis Set	Concomitant Medication
Table 15.5.1	Annualized Incidence Rate of Acute Pain Crisis – Safety Analysis Set (With Chronic Pain)	Subgroup
Table 15.5.2	Annualized Incidence Rate of Acute Pain Crisis – Safety Analysis Set (Without Chronic Pain)	Subgroup

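### PGIC is listed as change from the pre-Oxbryta period, but the supplied form asks about change since the start of the study, and Table 15.2.7 pools participants already on drug at consent with those who were not

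*Protocol*

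**What the plan says.** - **Endpoint.** SAP 3.2 places PGIC and CGIC under the heading "Change from pre-Oxbryta® (Voxelotor) treatment period in the following HRQoL measures". Protocol 8.1.1.2 does the same, and protocol 10.3.6.3.2 describes PGIC as reflecting the respondent's belief about how well Oxbryta works.
- **PGIC form** (protocol Appendix 2): "Compared to your condition at the start of the study, how much have you changed". It can be answered by the participant or by a parent as proxy.
- **CGIC form** (same appendix): "Compared to the subject's condition prior to treatment, how much has the subject's condition changed".
- **Who enters.** Current users and people about to start are both eligible (protocol 9.1.1.1 and 9.3.1). Follow-up runs to 5 years after first dose "Regardless of how long participants have been on Oxbryta® (Voxelotor) when they enroll in the study". SAP Figure 1 is titled for patients on treatment at consent, and SAP 4.2 and 4.4 provide for transfers from the RETRO study.
- **Candidate starting dates.** Protocol 9.14.2.1: "The first act of recruitment is the first site open and will be the study start date". SAP 4.7.1: "The index date is defined as the inform consent date". Protocol 9.7 begins data collection at the first commercial dose. None of these is tied to the PGIC question.
- **Analysis.** SAP 4.7.3: "The PGIC will be summarized as numbers and percentages by visit for each response category". The table is "Summary of Patient Global Impression of Change (PGIC) – Full Analysis Set". None of the subgroups in SAP 4.2.1 or 4.7.5 splits participants by treatment status at consent.

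**The concern.** PGIC has no baseline measurement. Appendix 1 schedules it from Month 3 onward only, so the reference point sits entirely in the wording of the question. For CGIC that wording matches the endpoint heading. For PGIC it matches only if the respondent takes the start of the study to be a time before treatment.

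For someone who consented on or before first dose, it is. For someone already on drug at consent, a reading as enrolment puts the reference after treatment began. Any benefit or harm felt before enrolment then drops out of the answer. The same row of Table 15.2.7 would hold answers to two different questions, and only one of them is the listed endpoint.

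The stake is interpretation, not an error rate. SAP 4.7.3 drops PROMIS from the report because responses were sparse. Table 15.2.7 is therefore the only patient-reported quality-of-life table in SAP Appendix A, within a report meant to support a benefit-risk evaluation. It sits beside the CGIC table, which uses the same seven categories and the same population but a different reference point. Without a note, readers will take both as change from before treatment.

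**Working it through.** The plan states no figure on this point, so there is none to reproduce. The check sets the readings side by side and then works out the time spans they imply.

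**1. Reference point by group and reading**

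| Group | Start of study = enrolment | Start of study = first dose |
|---|---|---|
| Consented on or before first dose | 0 to 6 months before dosing: pre-treatment | Pre-treatment |
| Already on drug t months at consent | On treatment, month t | Pre-treatment |

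The 6-month limit comes from SAP 4.2, which treats those not dosed within 6 months of consent as screen failures. Only one of the four cells departs from the endpoint. The site-opening date in protocol 9.14.2.1 is a study-level date that a respondent would hardly have in mind, so it is left out.

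**2. Span covered by an answer**

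Assumption: visit months count from first dose, which fits a last visit at Month 60 and follow-up to 5 years after first dose. At visit month m, an answer covers:

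- already on drug t months at consent, enrolment reading: m − t months, all on drug;
- the same participant, first-dose reading: m months;
- consented before first dose, enrolment reading: m to m + 6 months, from a pre-treatment state.

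At Month 12:

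- t = 6: 12 − 6 = 6 months, against 12;
- t = 9: 12 − 9 = 3 months, against 12;
- consented before first dose: 12 to 18 months.

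**3. How large t can be**

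Inputs: US approval in November 2019 (protocol 7.1.2) and start of data collection on 02 February 2022 (protocol 6).

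- 1 November 2019 to 02 February 2022: 824 days = 27.1 months.
- 30 November 2019 to 02 February 2022: 795 days = 26.1 months.

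A participant on commercial drug since approval could thus have t of about 26 to 27 months when data collection opened, and more if consented later, within the 5-year window. At Month 30 the enrolment reading gives 30 − 27.1 = 2.9 to 30 − 26.1 = 3.9 months, against 30 months from first dose.

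**4. What cannot be computed**

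The documents do not give the share already on drug at consent, how respondents read the question, or the answers. A participant t months on drug at consent can complete the registry questionnaire only at visits with m > t, so the mix also changes from row to row and no single share describes the table. A difference between the two groups would also reflect selection, because people still on drug at consent had tolerated and continued it. For these reasons no estimate of distortion in the percentage improved is offered.

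**The case against.** Several points on the other side have force.

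- **Not every relevant document is visible.** SAP Figure 1 covers exactly the affected group but is not shown, and the CRF completion guideline (protocol 9.12.1) is a separate document. Either may fix the reference point. A reader might infer that the starting point is flatly undefined. The documents do not support that; they support only that the visible text does not define it for a participant. This stands, and it makes the fix conditional.
- **A treatment-anchored reading is possible.** Protocol 10.3.6.3.2 ties PGIC to the effectiveness of Oxbryta, and protocol 9.7 starts data collection at first dose. But respondents see the form, not these sections, and the form does not mention treatment. Enrolment remains the more natural reading, though not a proven one.
- **The table does not itself claim change from pre-treatment.** SAP 4.7.3 gives PGIC its own bullet, and the title of Table 15.2.7 says only that it is a summary. The mismatch is with the endpoint heading in protocol 8.1.1.2 and SAP 3.2. That is right, and it is why a footnote does much of the work. It does not separate the two kinds of answer within a row.
- **Usual-care PGIC.** The supplied form is used only where PGIC is not already part of usual care, so the wording behind some answers is unknown. This adds to the need to state the reference point.
- **Low stakes.** PGIC is recommended rather than required (protocol 9.7), the report concentrates on laboratory values and clinical events, and neither a test nor a PGIC–CGIC comparison is planned. This stands and limits the weight of the point.

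**Conclusion.** The mismatch between the listed endpoint and the supplied PGIC question is in the documents' own words, and the planned table does not separate the participants for whom it matters. If respondents read the start of the study as enrolment, Table 15.2.7 does not report the listed endpoint for those already on drug at consent. At Month 12 such an answer could cover 3 or 6 months rather than 12 (t = 9 or 6), and for the earliest entrants at Month 30 about 3 to 4 months rather than 30.

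This rests on three assumptions: the enrolment reading, visits counted from first dose, and no instruction to respondents in the material we cannot see.

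Two stronger inferences are tempting. One is that PGIC as a whole is invalid. It is not: for anyone who consented on or before first dose, both participant-level readings give a pre-treatment reference. The other is that the pooled percentages are biased by some amount or in a known direction. The documents give neither the share affected nor any responses, so size and sign are unknown. It is a cheap improvement to a descriptive table and bears on no error rate.

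**What to change.** In SAP 4.7.3 and Appendix A:

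1. Footnote Tables 15.2.7 and 15.2.8 with the reference point as worded on each form.
2. Present PGIC by visit separately for (a) participants who consented to this registry on or before first dose, read as change from pre-Oxbryta, and (b) participants already on drug at registry consent, labelled as change since the start of the study and not read as change from pre-treatment.
3. Classify RETRO transfers by their consent date for this registry against their first dose.
4. The full analysis set includes screen failures, so show any never-dosed respondents separately or exclude them with a note.
5. State whether SAP Figure 1 or the CRF completion guideline told respondents that the reference is before first dose. If so, the footnote alone is enough.

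The split uses consent and first-dose dates and needs no new data. The cost is some table programming and less precision. With half of respondents improved, the exact (Clopper-Pearson) 95% half-width is:

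| Respondents (assumed split) | Pooled | Group (a) | Group (b) |
|---|---|---|---|
| 500 (350/150) | 4.5 points | 5.4 | 8.3 |
| 250 (175/75) | 6.4 | 7.6 | 11.8 |
| 100 (70/30) | 10.2 | 12.2 | 18.7 |

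Only the 500 comes from the documents, as planned enrolment; response numbers and splits are assumptions. If few respond, the smaller group will be imprecise, which the table should make plain by showing its denominators.

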10.3.6.3.2. Patient Global Impression of Change (PGIC)

Data from the self-reported Patient Global Impression of Change (PGIC) will be collected. The PGIC is a single question that reflects a participant's or caregiver's belief about the effectiveness of treatment with Oxbryta® (Voxelotor). PGIC is a 7-point scale depicting a participant's rating of overall improvement. Participants/caregivers rate their change as "very much improved," "much improved," "minimally improved," "no change," "minimally worse," "much worse," or "very much worse".

If not performed as part of the participant's usual care, the questionnaire will be provided.

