3. STUDY OBJECTIVES AND HYPOTHESES

3.1. Primary objectives

The primary objective is to gather long term data on Oxbryta® (Voxelotor) in a real-world setting. The following are outcome categories of interest in participants with SCD treated with Oxbryta® (Voxelotor):

- Clinical outcomes, as assessed by clinical and laboratory assessments of hematological parameters and end organ damage, and rate of significant clinical events
- Healthcare resource utilization (HCRU)
- Health-related quality of life (HRQoL), as assessed by participants, parents/caregivers, and clinicians
- Safety and tolerability of Oxbryta® (Voxelotor) Outcome Measures

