Bilirubin (Direct)	Effectiveness endpoint measures - Chemistry	Case report form	Captured from laboratory assessment-Chemistry form

Bilirubin (Indirect)	Effectiveness endpoint measures - Chemistry	Case report form	Captured from laboratory assessment-Chemistry form
Ferritin	Effectiveness endpoint measures - Chemistry	Case report form	Captured from laboratory assessment-Chemistry form
Albumin Creatinine Ratio (ACR)	Effectiveness endpoint measures – Renal function	Case report form	Captured from laboratory assessment- Renal function form
GFR	Effectiveness endpoint measures – Renal function	Case report form	Captured from laboratory assessment- Renal function form
Creatinine (Serum)	Effectiveness endpoint measures – Renal function	Case report form	Captured from laboratory assessment- Renal function form
Serum cystatin C	Effectiveness endpoint measures – Renal function	Case report form	Captured from laboratory assessment- Renal function form
Estimated eGFR	Effectiveness endpoint measures – Renal function	Case report form	Captured from laboratory assessment- Renal function form
Transfusions	Safety endpoint measures	Case report form	Captured from transfusions form
Patient Global Impression of Change (PGI-C)	Effectiveness endpoint measures	Case report form	Captured from Patient Global Impression of Change (PGI-C) form
Clinical Global Impression of Change (CGI-C)	Effectiveness endpoint measures	Case report form	Captured from Clinical Global Impression of Change (CGI-C) form
Pregnancy Testing and Fertility	Safety endpoint measures	Case report form	Captured from Pregnancy Testing and Fertility form
SCD Complications/Adverse Events	Safety endpoint measures	Case report form	Captured from SCD Complications/Adverse Events Question form
Pregnancy	Safety endpoint measures	Case report form	Captured from Pregnancy Notification and Outcome forms
Oxbryta Physician Administration	Exposure measures	Case report form	Captured from Oxbryta Physician Administration form

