4.7. Statistical methodology and analyses

The following general analysis will be followed for this study, unless otherwise specified.

Unless otherwise specified, continuous/quantitative variables will be summarized using descriptive statistics which will include the number of participants with data to be summarized (n), mean, standard deviation (SD), median, first and third quartile (Q1, Q3), minimum, maximum, and the number of missing observations. Minimum and maximum will be reported with the same number of decimal places as collected in raw data, while mean, median, Q1, Q3 will be reported with one extra decimal place, and SD will be reported with two extra decimal places. Descriptive statistics for categorical/qualitative variables will be presented with number of participants and percentage (%) of participants in each category.

Percentages will not include the missing category and will be calculated over the number of participants with available (non-missing) data. A category with a zero count will be presented as “0” and a category with a 100 percentage will be displayed as “100”.

The annualized incidence rate is defined as total numbers of a given event for all participants divided by the total patient-year where the total patient-year is defined as the sum of total duration (years) as defined in the Section 4.7.1 for all participants.

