4.7.3. Analyses for Effectiveness Endpoint Measures

Since this study was not designed as the efficacy study for different indications that contribute significant information about product safety, the analyses in the SAP are considered fit-for-purpose for an abbreviated clinical study report with data scope including 1) full safety data and 2) limited efficacy data to support the benefit-risk evaluation.

Given the reporting nature of the PROMIS items, the reported PRO response was sparse. Therefore, they were excluded from the planned CSR analyses.

The analyses for effectiveness endpoints are based on full analysis set (Section 4.2). The analyses for the abbreviated CSR focus on hematologic and renal function laboratory parameters and SCD-related clinical events.

Participant disposition, non-SCD medical history, concomitant medication, study drug administration (including dosage changes initiated by the participant and by the physician), demographics and baseline characteristics will be summarized descriptively based on full analysis set.

The descriptive statistics will be provided for the following medications:

- long-acting opioids
- Erythropoiesis-stimulating agents
- Other relevant pain meds (e.g. Gabapentin, Lyrica, Cymbalta)
- SCD disease modification agents (hydroxyurea, Adakveo/crizanlizumab, L-Glutamide/levoglutamide).

The study drug administration will be categorized as 1) < 1 month, 2) >=1, <2 months, 3) < 3 months, 4) >=3 months, < 6 months, 5) >=6 months, < 9 months, 6) >=9 months, < 12

months, 7) ≥ 12 months, < 18 months, 8) ≥ 18 months, < 24 months, 9) ≥ 24 months, < 36 months, 10) ≥ 36 months, < 48 months and 11) ≥ 48 months.

The following effectiveness endpoints will be summarized descriptively:

- Change from pre-Oxbryta treatment period in the following hematologic parameters corresponding to treatment with Oxbryta® (Voxelotol):
 - Hb
 - Hemolysis measures, including % reticulocytes, absolute reticulocytes, bilirubin (total, direct, and indirect)
 - ALT and AST

Analysis: Observed and change from pre-Oxbryta treatment period on Hb, Hemolysis measures will be summarized descriptively ([Section 4.7](#)) by visit

If a queried hemolysis value remained greater than its threshold listed in the table below, the value would be deemed erroneous and excluded from the analysis,

Parameter	Threshold
Reticulocyte Count (absolute)	10,000 $10^{9}/L$
Ferritin	100,000 $\mu g/L$

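### PGIC is planned as one by-visit summary with no split by rater, so the caregiver ratings it contains cannot be identified, although the form records who rated

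*Protocol*

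**What the plan says.** - Protocol Appendix 2, PGIC form: after the seven-point rating, the form asks "How has this assessment been performed" and allows two answers, self-report by the participant or proxy report by a parent.
- Protocol 10.3.6.3.2: "The PGIC is a single question that reflects a participant's or caregiver's belief about the effectiveness of treatment". Either may rate. No age rule decides who does, and nothing asks for the same rater over time.
- SAP 3.1 lists among its outcome categories "Health-related quality of life (HRQoL), as assessed by participants, parents/caregivers, and clinicians".
- SAP 4.3 defines the PGIC variable only as "Captured from Patient Global Impression of Change (PGI-C) form", with no rater variable.
- SAP 4.7.3: "The PGIC will be summarized as numbers and percentages by visit for each response category". Appendix A has one matching output, Table 15.2.7, "Summary of Patient Global Impression of Change (PGIC) – Full Analysis Set".
- SAP 4.7.3 on PROMIS, after describing the responses as sparse: "Therefore, they were excluded from the planned CSR analyses".
- SAP 4.7: percentages are "calculated over the number of participants with available (non-missing) data".

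**The concern.** Enrolment is open from age 4, so some ratings are likely to come from parents. The registry collects the field that separates these from participants' own ratings, but the analysis plan does not use it. Two things follow.

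First, the primary objective names three kinds of assessor, and after the removal of PROMIS the planned CSR has no output in which the caregiver's view can be recognised.

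Second, each by-visit percentage may average two kinds of rater in proportions that the table does not show. A reader who compares month 6 with month 48 could not tell a change in how participants are doing from a change in who answered.

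**Working it through.** **Step 1. Is caregiver-assessed HRQoL identifiable anywhere in the planned outputs?**

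| Measure | Rater, per protocol | Planned CSR output |
|---|---|---|
| PROMIS, including the Parent Proxy Profile | participant or caregiver | none; excluded in SAP 4.7.3 |
| PGIC | participant or caregiver | Table 15.2.7, no rater split named |
| CGIC | clinician (Protocol 10.3.6.3.4) | Table 15.2.8 |
| NPRS | participant, asked verbally (Protocol 10.3.6.3.3) | none in Appendix A |

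The subgroups in SAP 4.2.1 and 4.7.5 concern chronic pain, Hb increase and populations for the pain-crisis/VOC rates. None is by rater or age, and none is applied to PGIC. Proxy PGIC is therefore the only caregiver-assessed HRQoL remaining, and no planned output identifies it. This step needs no assumption about the data.

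**Step 2. What does an unsplit percentage do across visits?**

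The documents state no PGIC percentage or proxy share, so there is no figure of theirs to reproduce. Let w be the proxy share at a visit, and p_proxy and p_self the percentages rated improved by each kind of rater.

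- Combined percentage = w × p_proxy + (1 − w) × p_self
- If p_proxy and p_self stay constant, change between visits = (w_late − w_early) × (p_proxy − p_self)

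Illustration with assumed inputs: p_self = 50%, p_proxy higher by the gap shown, early proxy share 40%. If proxies rated lower, the signs would reverse.

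| Rater gap | Share 40% → 30% | 40% → 20% | 40% → 10% |
|---|---|---|---|
| 0 points | 0 | 0 | 0 |
| 10 points | −1.0 | −2.0 | −3.0 |
| 20 points | −2.0 | −4.0 | −6.0 |
| 30 points | −3.0 | −6.0 | −9.0 |

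One cell in full: early 0.40 × 70 + 0.60 × 50 = 58%; late 0.20 × 70 + 0.80 × 50 = 54%; shift −4 points.

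**Step 3. Could ageing alone change the share?**

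Assume a fixed cohort that always responds, paediatric ages spread evenly over 4 to <18 at first dose, and proxy rating below age 12. None of this is in the documents. Among children, the proxy share is then 8/14 at first dose and 3/14 five years later.

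| Paediatric share of cohort | Proxy share, first dose → month 60 | Shift at gaps of 10 / 20 / 30 points |
|---|---|---|
| 20% | 11.4% → 4.3% | −0.7 / −1.4 / −2.1 |
| 40% | 22.9% → 8.6% | −1.4 / −2.9 / −4.3 |
| 60% | 34.3% → 12.9% | −2.1 / −4.3 / −6.4 |

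PGIC is first scheduled at month 3, so this slightly overstates the observable span.

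**Step 4. Scale.** The 95% half-width of one proportion near 50% is 1.96 × √(0.25/n): 4.4 points at n = 500, 6.2 at n = 250 and 9.8 at n = 100. Most of the illustrated shifts are no larger than ordinary sampling error at plausible visit sizes.

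**The case against.** The strongest reply is that nothing has been shown to be wrong. No SAP sentence says that raters are combined. Appendix A gives titles without shells, so the absence of a split is inferred from silence. A combined summary also fits the protocol's definition of PGIC as a participant's or caregiver's view, and Protocol 8.1 evaluates objectives only where data are available. The analysis is descriptive, with no test, model or trend, in an abbreviated CSR centred on laboratory parameters and SCD events. HRQoL forms are recommended and not required (Protocol 9.7), so splitting seven categories over 12 visits may leave very small cells.

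Much of this stands, and it limits what can be claimed. Three stronger readings are tempting and not supported:

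- *Caregiver ratings go unreported.* They are counted in Table 15.2.7; they are just not distinguishable.
- *Proxy opinion is passed off as patient-reported.* The word Patient is part of the instrument's name, and the protocol openly allows caregiver raters.
- *Rater changes at 18 are built into follow-up.* With ages even over 4 to <18, 5/14 = 36% of children would pass 18 within five years. But no text ties proxy rating to being under 18. A paediatric self-report PROMIS form is supplied beside the parent-proxy form, and assent is sought from age 12, so teenagers may self-report throughout. Participants already on treatment at enrolment are also observed for less than five years.

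What the reply does not answer is Step 1: the objective names caregivers, the form identifies them, and the listed outputs do not.

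**Conclusion.** The point holds as a modest, inexpensive improvement. Followed as written, the plan yields no identifiable caregiver-assessed HRQoL result, and its by-visit PGIC percentage does not distinguish two kinds of rater. That rests on the text alone, with the caveat that the missing split is read from silence.

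The shift across visits is a possibility and not a demonstrated bias. It needs both a rater gap and a changing proxy share. Follow-up of up to five years from age 4, optional questionnaires, responder-only denominators and the absence of a rater rule make a changing share plausible, but its size cannot be computed from the documents. The illustrations give 0 points if raters agree, 1 to 9 points for gaps of 10 to 30 points with share falls of 10 to 30 points, and 0.7 to 6.4 points from ageing alone under the stated assumptions. None of these should be quoted as an estimate for this registry.

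**What to change.** In SAP 4.7.3 and Table 15.2.7, present PGIC by visit in separate columns for participant self-report, parent proxy and rater not recorded, each with its own denominator. Keep the combined column as secondary. Flag participants whose rater changes during follow-up, and state that differences between visits should not be read across such a change. Add the rater to the variable list in SAP 4.3.

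The not-recorded column is needed because, on the form as extracted, the rater item lacks the asterisk that its neighbours carry. If the asterisk marks mandatory items (an assumption), some records may have no rater.

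No new data are required. The cost is a short SAP addition, a by-variable in one table and a derived flag. The drawback is sparser cells: 7 categories × 12 visits = 84 per rater column. Keeping the combined column softens this, and the rater denominators would at least show how much caregiver data exists.
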